#### 8.7.f Determination of whether or not an Adverse Event is Serious.

In the course of completing the adverse event forms, it will be determined whether or not it is a serious adverse event (see the definition in 8.7.a).

#### 8.7.g Time period and frequency for event assessment and follow up.

The occurrence of an adverse event (AE) or serious adverse event (SAE) may come to the attention of study personnel during study visits and interviews of a study participant presenting for medical care, or upon review by a study monitor.

All AEs including local and systemic reactions not meeting the criteria for SAEs will be captured on the appropriate case report form (CRF) in RedCap. Information to be collected includes event description, time of onset, [name] assessment of severity, relationship to traction versus standard orthosis, and time of resolution/stabilization of the event. All AEs occurring while on study must be documented appropriately regardless of relationship. All AEs will be followed to adequate resolution. For an expected AE, follow up for 30 days after the onset of the AE will be considered as an adequate resolution.

Any medical condition that is present at the time that the participant is screened will be considered as baseline and not reported as an AE. However, if the study participant's condition deteriorates at any time during the study, it will be recorded as an AE.

Changes in the severity of an AE will be documented to allow an assessment of the duration of the event at each level of severity to be performed. AEs characterized as intermittent require documentation of onset and duration of each episode.

Our Research Coordinator, [name], will record all reportable events with start dates occurring any time after informed consent is obtained until 7 (for non-serious AEs) or 30 days (for SAEs) after the last day of study participation. At each study visit (including in clinic visits and weekly telephone calls), the investigator will inquire about the occurrence of AE/SAEs since the last visit. Events will be followed for outcome information until resolution or stabilization.

## **8.8 Unanticipated Problem Reporting**

**Unanticipated Problem** – defined by OHRP as any incident, experience or outcome that meets **ALL** the following requirements:

1. **Unexpected** (in terms of nature, severity, or frequency) given (a) the research procedures that are described in the IRB-approved research protocol and informed consent document; and (b) the characteristics of the population being studied.
2. **Related or possibly related to participation in the research**. Possibly related means there's a reasonable possibility that the incident, experience, or outcome may have been caused by the procedures involved in the research.
3. Suggests that the **research places participants or others at a greater risk of harm** (including physical, psychological, economic, or social harm) than was previously known or recognized.

[figure not shown]
[figure not shown]

Figure 8. Flowchart indicating the determination of whether an adverse event is an unanticipated problem.

To be clear, only a SMALL number of serious adverse events will fit into this category. Additionally, there are situations not considered adverse events that can be considered an unanticipated problem.

The following Venn diagram summarizes the general relationship between adverse events and unanticipated problems:

6. [name] will also report the Unanticipated Problem to the MEDVAMC Research Office, the Privacy Officer, and the Facility Research Compliance Officer **within 5 business days** of becoming aware of the event, according to VA Research and Development requirement.
7. **[name] will review all unanticipated problems on a weekly basis** until there is **resolution of the event or completion of the study**. During each review, she will re-review whether there needs to be modification of the study intervention.

## 9.0 Statistical Considerations

*Because this is a pilot study, we do not plan to adjust for multiple comparisons.*

**Specific aim 1. Feasibility of a static hand based orthosis to apply finger traps.** We will calculate means and standard deviations for VAS scores for comfort level while wearing the orthosis ease/difficulty of donning the orthoses, how well they like the orthoses, and overall hand pain using visual analog scales (VAS), providing scores from 0 -10 at the 1 month, 3 month, and 6 month follow up visits.

**Specific aim 2. Proof of concept.** We will pair the radiographs of the hands with and without orthoses applied to subjectively assess whether the traction orthoses result in an improvement in joint space narrowing score. Because will only be performing these measures on 10 participants, we will not run formalized statistics on these comparisons.

**Specific aim 3. Symptomatic and functional outcomes.** Because this is a pilot study, we will be broad in our inclusion of outcome measures of interest with the understanding that these findings will help to inform our future outcome measure choices to select for follow up studies of traction therapy. Our primary outcome measures of interest will be overall hand VAS pain. Other outcome measures will include AUSCAN pain, VAS pain and tenderness in the most symptomatic joint and of all DIPs. For functional outcomes, we will evaluate the AUSCAN function subscale, the Functional Index for Hand Osteoarthritis (FIHOA), the Disabilities of the Arm, Shoulder, and Hand (DASH), the Functional Dexterity Test, grip and pinch strength.

We will complete descriptive analyses of baseline characteristics of the treated and control groups to allow assessment of generalizability and success of randomization. We will use either Student t-tests or rank-based nonparametric tests where appropriate. Our primary analytic approach will be to use intention- to-treat (ITT) analyses to compare mean change of each symptom and function outcome during follow-up between traction therapy and the control groups with linear regression model for longitudinal repeated measures data. Missing outcomes among participants who missed pain and function questions or lost to follow up will be addressed by multiple imputation using the Markov chain Monte Carlo method. Under the assumption of missing at random, we will include factors which may be related to missing of outcome in the imputation, such baseline demographic characteristics, disease severity, etc. We can use this method of imputation because all outcomes are continuous and they can be assumed to follow multivariate normality distribution. To use this method of multiple imputations, there is an assumption of missing at random. Though this assumption is not testable, multiple imputation method are viewed as less biased than a completers' analysis, last observation carried forward, and single imputation method.

**Specific aim 4. Imaging outcomes.** Given the exploratory nature of this study, we will be broad in our inclusion of outcome measures we will evaluate. The primary structural outcome measure will be change in sum of the Kellgren and Lawrence score of all DIPs in the hand that was braced. We will also evaluate change in joint space narrowing, and osteophyte scores and the Verbruggen-Veys from baseline to 6 month follow up comparing the traction versus the control groups. For those randomized to traction, we will also compare the hand that received traction to the hand that did not. To address potential missing data, we will use a multiple imputation method, assuming the data are missing at

random. We will perform an ANOVA to compare mean change in the sum of radiographic scores over the 6 month follow up period between the traction therapy and the control groups. If there are unbalanced baseline covariates between the treatment groups, we will use an ANCOVA approach to include them as covariates in the analysis.

**Power calculation:** Assuming the SD of change in the summary score is 3, we can expect at least 80% power to detect a difference of 1.7 in the change of the summary score between the two arms with 100 participants (50 in each arm) for a two-sided type 1 error rate of 5%.

On 5 participants in each treatment arm (age and sex matched) for whom we will have high resolution MRI imaging at baseline and at 6 months, we will plot the measurements for collateral ligament thickening, enthesial bone marrow edema, and erosions of the most symptomatic DIP at baseline and then at 6 months to see if we can identify any differences by visual inspection.

[figure not shown]

Figure 10. Power curve for change in the DIP summary score change in finger traction v. control groups.

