### 3.0 Study Objectives

**Specific aim 1. Feasibility of a static hand based orthosis to apply finger traps.** The study OT will customize a static hand based orthosis that allows convenient application of finger traps for those receiving traction. We will record issues related to creating the traction orthoses, ease/difficulty of applying the intervention, comfort level while wearing the orthosis, hand pain, and compliance of wearing the orthosis. At the final study visit, we will also ask whether participants plan to use the orthosis after completion of the study.

**Specific aim 2. Proof of concept.** For 10 participants, 5 participants in each arm that are age and sex matched, at the two week follow up, we will obtain radiographs of the hand *with* and *without* orthoses applied to assess whether applying the traction orthosis results in an increase in joint space width.

**Specific aim 3. Symptomatic and functional outcomes.** At baseline, 1 month, 3 months, and 6 months follow up, we will assess outcomes including the visual analog scale (VAS) in the more symptomatic hand that includes the most symptomatic DIP joint (primary symptom outcome), the VAS pain scale of the most painful DIP, the AUSCAN function subscale, the Functional Index for Hand Osteoarthritis (FIHOA), the Disabilities of the Arm, Shoulder, and Hand (DASH), the Functional Dexterity Test, grip and pinch strength, and tenderness on joint palpation on all participants.

**Specific aim 4. Imaging outcomes.** On all participants, we will obtain bilateral hand radiographs at baseline and at 6 months to assess changes in Kellgren and Lawrence scores (primary structure outcome), joint space narrowing, and osteophyte scores, and Verbruggen-Veys in the DIP joints. On 5 participants in each treatment arm (age and sex matched), we will obtain high resolution MRI imaging at week 2 and at 6 months to evaluate collateral ligament thickening, enthesial bone marrow edema, and erosions of the most symptomatic DIP.

OBJECTIVES	ENDPOINTS	JUSTIFICATION FOR ENDPOINTS
Primary		

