## 4.0 Study Design

**4.1 Overview of the Proposed Study.** This is a pilot randomized controlled clinical trial (n=40) of finger traction therapy in the treatment of nodal hand OA where the control arm will receive the standard of care and the treatment arm will additionally use a finger traction orthosis.

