## **8.2. Symptom Efficacy Assessments**

All of the following assessments will be made by our Research Coordinator and itemization of the data will be collected in RedCap. These will include:

Outcomes: (Assessed at the baseline, week 4, week 12, and week 24 visits)

- the VAS pain scale, asking about pain in the hand that includes the most symptomatic DIP over the last 48 hours (primary outcome)
- Australian Canadian Hand OA Index (AUSCAN) pain scale, (although we have requested copyright permission to use the scale, we have yet to receive permission to do so – we plan to administer the outcome, but if not given permission, we will not publish with this data).
- the VAS pain scale, asking about pain in the most symptomatic DIP in the last 48 hours,
- the AUSCAN function subscale,
- the Functional Index for Hand Osteoarthritis (FIHOA)
- the Disabilities of the Arm, Shoulder, and Hand (DASH),
- the Michigan Hand Outcomes,
- the Functional Dexterity Test,
- grip and pinch strength, and
- tenderness on joint palpation on all hand joints.
- photographs of the participant's hands
- We will also take a medication inventory (dichotomous assessments)
  - i. Pain medications (e.g. acetaminophen, all non-steroidal anti-inflammatory medications, and opioid medications).
  - ii. Glucosamine and chondroitin
  - iii. Marijuana use

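### The Aim 3 analysis of change in hand VAS pain does not specify adjustment for the baseline value; adding it would gain precision at almost no cost

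*Combined protocol and SAP*

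**What the plan says.** Section 9.0, Specific aim 3, sets an intention-to-treat analysis that will "compare mean change of each symptom and function outcome during follow-up between traction therapy and the control groups with linear regression model", fitted to the repeated measurements over time. It lists no model terms: no visit effect, arm-by-visit term, covariance structure or covariate.

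Section 8.2 names pain in the whole hand over the last 48 hours, on a VAS, as the primary symptom outcome. It schedules that and the other symptom and function outcomes alike: "Assessed at the baseline, week 4, week 12, and week 24 visits". Section 3.0, Specific aim 3, gives the same times in months.

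Baseline variables have two uses in Aim 3. They are described by arm, to judge generalizability and the success of randomization, and they enter the imputation model, "such baseline demographic characteristics, disease severity, etc". The one adjustment rule in section 9.0 stands under Specific aim 4, after the ANOVA of radiographic scores: "If there are unbalanced baseline covariates between the treatment groups, we will use an ANCOVA approach to include them as covariates in the analysis".

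On size, section 4.1 states: "This is a pilot randomized controlled clinical trial (n=40) of finger traction therapy". Section 6.2 stratifies randomization by sex only.

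**The concern.** A between-arm comparison of change subtracts the whole baseline value from follow-up, which fixes the baseline slope at 1. Follow-up pain usually relates to baseline with a slope below 1, so full subtraction over-corrects and puts part of the baseline noise into the estimate.

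The repeated-measures form does not remove this by itself. If baseline is the first response and each arm has its own baseline mean, the arm-by-visit contrast is still the difference in mean change. The loss is recovered only with baseline as a covariate, or with a baseline mean constrained to be common to both arms. The plan specifies neither.

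What is at stake is precision in a trial of 40. Section 2.8 says that effect sizes from this study will feed the power calculations for the follow-up trial. A wider interval, or an estimate moved by a chance difference in baseline pain that randomization does not balance by design, makes a poorer planning figure.

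**Working it through.** **The plan's own figure.** The only power statement (section 9.0) is for the radiographic summary score: SD 3, difference 1.7, 50 per arm, two-sided 5%, at least 80%. It reproduces (0.809 by the normal approximation, 0.801 by the noncentral t). It concerns neither VAS pain nor 20 per arm, so it cannot size this point.

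**Inputs.** From the documents: N = 40, taken as 20 per arm; visits at baseline and weeks 4, 12 and 24; two-sided 5%, borrowed from the structural power statement. Assumed, because the documents are silent: equal SDs at baseline and follow-up, and rho from 0.3 to 0.8. The starting powers of 50% and 80% are reference points; the plan claims no power for VAS.

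**Single visit, unit variance.**
- Variance of change: 2(1 − rho)
- Variance after baseline adjustment: 1 − rho²
- Ratio, adjusted to change: (1 + rho)/2, so the cut is (1 − rho)/2

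Power is from the noncentral t. With 38 df, 50% and 80% power on change need noncentralities of 2.011 and 2.875. For the adjusted analysis these are divided by √[(1 + rho)/2 × 38/37], with 37 df. At rho 0.5: 2.011/√(0.75 × 38/37) = 2.29, which gives 61%.

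| rho | change | adjusted | cut | 50% becomes | 80% becomes |
|---|---|---|---|---|---|
| 0.3 | 1.40 | 0.91 | 35% | 67% | 93% |
| 0.5 | 1.00 | 0.75 | 25% | 61% | 89% |
| 0.7 | 0.60 | 0.51 | 15% | 55% | 85% |
| 0.8 | 0.40 | 0.36 | 10% | 53% | 83% |

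Simulation (20,000 trials, 20 per arm) gave variance ratios of 0.66, 0.77 and 0.87 at rho 0.3, 0.5 and 0.7. These are slightly above 0.65, 0.75 and 0.85 because the slope has to be estimated.

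**Entry floor.** Section 5.3 requires a VAS of at least 40, listed under pain of at least one DIP joint. The primary outcome is whole-hand pain, so how far the floor truncates it is unknown. The limiting case puts the floor directly on baseline hand VAS. Let k be the truncated baseline variance as a fraction of the untruncated one. The cut becomes (1 − rho)k / [(1 − rho)k + 1 + rho]. Assume an untruncated mean of 50–60 and SD of 20–22:
- Mean 50, SD 22: k = 0.474. At rho 0.6 the cut is 0.190/1.790 = 11%.
- Mean 60, SD 20: k = 0.630. At rho 0.5 the cut is 0.315/1.815 = 17%.
- Over all settings: about 11–17% at rho 0.5–0.6, or 9–15% if values are also capped at 100; about 7–10% at rho 0.7.

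An 11% cut moves 50% power to about 53% and 80% to about 83%. A 17% cut moves them to about 56% and 86%.

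**Chance imbalance.** Let D be the baseline difference, traction minus control. Given D, the expected follow-up difference is the effect plus rho × D. Subtracting D leaves the effect minus (1 − rho)D. The simulated slopes on D were −0.70, −0.50 and −0.30 at rho 0.3, 0.5 and 0.7, and about 0 after adjustment. With an assumed baseline SD of 20 mm, D has SD 20 × √(2/20) = 6.3 mm; at rho 0.5 half of D enters with its sign reversed. For baseline SDs of 15 to 25 mm, the 95% range of D is about ±9 to ±15 mm, which at rho 0.5 moves the estimate by up to about 5 to 8 mm.

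**Average of three visits (secondary).** Under compound symmetry, the variance of change is (1 + 2rho)/3 + 1 − 2rho and the adjusted variance is (1 + 2rho)/3 − rho². At rho 0.5 these are 0.667 and 0.417, a cut of 37.5%; 50% power becomes 69% and 80% becomes 94%.

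**The case against.** The strongest reply is that the plan is silent rather than wrong. A linear regression for repeated measures could contain baseline as a covariate or a common baseline mean, and nothing in Aim 3 forbids either. A reader might infer that the plan rules adjustment out; the text does not support that. What stands is that adjustment is not specified, and a covariate choice left until the data are in is what a plan should settle beforehand.

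A reader might also infer that the estimate is biased. It is not. Change scores use the baseline value, and over repeated randomizations the estimate is unbiased. The imbalance effect is conditional on the trial actually run, is partial, and runs opposite to the imbalance.

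On size, the reply is largely right. No VAS SD, rho or power target is given, and the floor of 40 could shrink the gain well below the untruncated figures. The three-visit figures are the largest, but the primary symptom endpoint in section 3.0 is framed by 24 weeks, so the averaged contrast may not be the primary one.

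Finally, this is a pilot that defers efficacy to a larger trial. That limits the seriousness. It does not remove the reason to adjust, because the effect estimate is one of the pilot's intended products and the change costs almost nothing.

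**Conclusion.** The point holds as an improvement in precision that is close to free, not as an error of validity. Aim 3 does not specify adjustment for the baseline value, no other section supplies it, and the conditional ANCOVA of Aim 4 does not reach these outcomes.

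At a single visit with 20 per arm, the variance reduction runs from about 35% at rho 0.3 to 10% at rho 0.8. It falls to about 7–17% over rho 0.5–0.7 if the entry floor bears fully on hand VAS. All these figures rest on an assumed rho and equal SDs; the truncated ones also rest on an assumed baseline mean and SD. None should be quoted as this trial's own loss of power. The gain shrinks in the less favourable settings but does not reverse in any setting examined.

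**What to change.** In section 9.0, Specific aim 3, add that the repeated-measures model includes the baseline value of the same outcome and its interaction with visit, for the primary hand VAS and every other Aim 3 outcome, regardless of observed imbalance.

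The comparison of change need not be replaced. With baseline in the model, analysing change or the follow-up value gives the same treatment effect; only the baseline coefficient differs, by 1. A model with a common baseline mean for both arms is an approximately equivalent alternative. Raw mean change by arm can remain as a descriptive summary.

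The cost is the wording and one degree of freedom per visit, which the single-visit power figures already allow for. No data, staff or participants are added.

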To address possible sex differences in the use and efficacy of the intervention, we will make a concerted effort to ensure the study sample is similar to the larger hand OA population in terms of gender. To operationalize this recommendation, we base our target recruitment on Framingham data where age-standardized prevalence of symptomatic hand OA in women and men respectively were 15.9% and 8.2%. Thus, we will oversample women in our VA at a ratio of 2:1, women : men to replicate a similar gender distribution to increase the generalizability of our findings. Our primary strategy for oversampling women is that we will use patient lists from the Women's Health Clinics to identify women who have upcoming visits to at our VA who are more likely to have hand OA. This will include women who have had hand x-rays that show evidence of hand OA and all who are over 60 years old. We will intentionally exclude those who carry a diagnosis of an inflammatory arthritis on their problems list or have a prior history of a hand surgery. To recruit the remainder of our population, we will similarly screen the geriatrics clinic and regular primary care clinics to invite those participants into our study.

**Telephone or E-mail Screen.** We will perform the telephone or e-mail pre-screen for all people who initiate contact with our study using traditional recruitment strategies as well as all those people identified from clinic panels who did not opt out of a contact from our study.

For all potential participants for whom we have contact with, our Research Coordinator, [name], will administer the "**Telephone Screening Survey**," on RedCap. However as these people will not yet have consented none of these responses will be saved on RedCap. If they pass the survey as possibly being eligible, [name] will maintain their names and contact information on a separate Excel Spreadsheet entitled "**PreEnrollment Tracker**" (**Appendix G**) and invite them to attend an in-person eligibility evaluation visit. At the beginning of the visit, our Research Coordinator will obtain informed consent to conduct study activities. Once that is completed, then the "Screening Survey" will be administered at which time the information can and will be saved and stored on RedCap.

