## **6.2 Randomization.**

Our Research Coordinator will contact our Statistician, [name], who will provide randomization allocation. [name] will use a macro in SAS that uses CALL RANUNI and PROC PLAN to generate permuted blocks of randomization stratified by sex.

- He will create a designation of group A v. group B, without knowing which group represents the intervention and the control.
- He will use block sizes of 4 for this process.

[name] will then communicate to our Research Coordinator and our OT that the treatment allocation has been entered onto RedCap.

Our statistician, [name], and our research coordinator will be blinded to treatment assignment. Only our OT will be unblinded to treatment allocation.

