Although hand OA is very common, only a small percentage seek care from their providers for this condition. Therefore, engagement into medical care for hand OA will be useful as a retention strategy. Additionally, participants will all receive durable goods to provide the standard of care for hand OA including a thermal modality and the orthoses made for them by our OT. Also, they will be instructed on range of motion exercises and joint protective strategies that should help their hand symptoms.

Regarding special vulnerable populations, fetuses, neonates, and children will not be eligible for this study because we are targeting veterans who are patients at the MEDVAMC. Pregnant women will be excluded to mitigate any potential risks related to radiation exposure associated with obtaining radiographs and high powered magnetic fields related to obtaining MRIs. We do not expect that prisoners or institutionalized individuals will learn about this study and therefore will not be recruited into the study. Therefore, no vulnerable populations will be included in this study so none of these groups will be placed at increased risk relative to other participants included in our study.

Once a participant is deemed eligible for participation into the study and is consented for the study, he/she will have all his/her baseline assessments administered by the study research coordinator. After this is completed, the research coordinator will email [name], our statistician, who will generate a randomization assignment (designated as group A v. group B) stratified by gender. This allocation assignment will only be transmitted to our OT by email after the OT has also seen the participant at baseline and provided all other non-pharmacologic interventions for hand OA that are considered standard of care. Prior to the beginning of the study, the OT will use a coin flip to decide which group (A v. B) will be the treatment v. control group. The OT will be the only person in the investigative team to know this

designation until the study data set is closed and all analyses are finalized. At that point, the OT will customize the appropriate orthosis for the participant to take with him/her.

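### Randomisation is stratified by sex, but Section 9.0 does not specify sex as a term in either primary analysis

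*Combined protocol and SAP*

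**What the plan says.** **Randomisation.** Under Section 6.2 the statistician will "generate permuted blocks of randomization stratified by sex". On block size the section says: "He will use block sizes of 4 for this process". Section 10.7.a repeats the scheme, with the statistician as the person "who will generate a randomization assignment (designated as group A v. group B) stratified by gender". No other stratification factor is named.

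**Sex mix.** Section 5.1 plans the recruitment: "we will oversample women in our VA at a ratio of 2:1, women : men".

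**Aim 3 analysis.** Section 9.0 compares mean change in each symptom and function outcome "between traction therapy and the control groups with linear regression model for longitudinal repeated measures data". It lists no model covariates. Baseline demographics appear only as inputs to the multiple imputation.

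**Aim 4 analysis.** Section 9.0 states: "We will perform an ANOVA to compare mean change in the sum of radiographic scores over the 6 month follow up". It then allows an ANCOVA, but only for baseline covariates that turn out to be unbalanced between the arms.

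**Covariate list.** Section 8.3 includes sex among the covariates of interest. The stated uses are to check the randomisation and to look for possible mediators.

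**The concern.** Blocking within sex holds the two arms close to the same sex mix, so differences between women and men add almost nothing to the true sampling variance of the arm comparison. A model without sex does not know this. It leaves any between-sex variation in the residual and reports a standard error for a less efficient design than the one used. The usual practice is to analyse with the factor that was used to randomise.

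The Aim 4 clause on unbalanced covariates does not fill the gap. It looks for imbalance, and sex is the one variable the design protects from imbalance. Aim 3, which carries the primary symptom endpoint, has no such clause.

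At stake are some power and interval width in a 40-person trial, and a modelling choice left open until the data are in hand.

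**Working it through.** **1. The plan's own power figure.** Section 9.0 gives SD of change 3, difference 1.7, 50 per arm, two-sided 5%, power at least 80%. A two-sample calculation gives 80.9% (normal approximation) or 80.1% (noncentral t, 98 df), so the figure reproduces without any covariate. At the planned 40 participants (20 per arm), the same t calculation gives 41.6%.

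**2. How unbalanced can sex be?** Blocks of 4 limit the arm difference to 2 people in each sex. A 2:1 mix of 40 is about 27 women and 13 men. Since 27 = 6×4 + 3 and 13 = 3×4 + 1, each stratum would end exactly one person out of balance. The unbalanced-covariate trigger would not reasonably pick that up.

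**3. Size of the standard error excess.** Let g be the difference between women and men in mean change, in within-sex SD units (assumed, since the documents give none). With p = 27/40, p(1−p) = 0.675×0.325 = 0.219. Under exact balance, the model SE without sex exceeds the true SE by the factor √(1 + 0.219g²). At g = 0.5 this is √1.055 = 1.027. At g = 0.8 it is √1.140 = 1.068. In simulation at g = 0.8 the excess is about 6%, slightly less because the strata are each one person off.

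**4. Simulation, treatment effect 0.8 within-sex SD (assumed).** N = 40, 27 women and 13 men, blocks of 4 within sex, one normal outcome, least squares with and without sex:

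| g | Power without sex | Power with sex | Loss (points) | Type I error without sex |
|---|---|---|---|---|
| 0 | 68.5% | 68.2% | about 0 | about 5% |
| 0.3 | 68.3% | 68.9% | 0.6 | 4.8% |
| 0.5 | 67.2% | 69.1% | 1.9 | about 4.5% |
| 0.8 | 63.6% | 68.5% | 4.9 | 3.6% |
| 1.0 | 61.3% | 69.5% | 8.2 | 3.3% |

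Repeat runs move the powers by up to about 1 point and the losses by less than half a point.

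**5. Simulation on the plan's own scale.** Difference 1.7 and total SD 3 (1.7/3 = 0.57 SD), N = 40, g now in total-SD units, 20,000 runs per setting:

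| g | Power without sex | Power with sex | Type I error without sex | Type I error with sex |
|---|---|---|---|---|
| 0 | 41.3% | 41.2% | 4.9% | 4.9% |
| 0.3 | 41.5% | 42.3% | 4.8% | 5.0% |
| 0.5 | 40.7% | 43.0% | 4.4% | 5.1% |
| 0.8 | 40.5% | 46.6% | 3.8% | 5.2% |
| 1.0 | 39.8% | 50.3% | 2.8% | 4.9% |

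At g = 0.8 the mean model SE without sex is 0.946 against a true spread of 0.891 (ratio 1.06). With sex it is 0.875 against 0.887.

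**6. Cost if sex does not matter.** By formula, at g = 0 and 20 per arm, power goes from 41.6% to 41.5%.

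**7. Precision of a by-sex contrast.** The SE of the treatment-by-sex interaction is √(4/27 + 4/13) = √(0.148 + 0.308) = 0.68 SD.

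**The case against.** The strongest reply is that the harm is conditional and mild. Both aims analyse change, so a stable difference in level between women and men cancels, and only a sex difference in change over 24 weeks matters. The documents report none. Up to 0.3 SD the loss is under 1 point of power, and the larger scenarios have no support in the text. The error is on the safe side, the trial is a pilot, and adequately powered efficacy testing is left to the follow-up trial. All of this stands, and it limits the weight of the point. It does not remove the point, because adjustment costs almost nothing when sex is irrelevant.

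A second reply is that Section 9.0 is silent on Aim 3 covariates and does not exclude sex, and that Section 8.3 lists sex as a covariate of interest. That is also right: the fault is that the model term is not specified. Silence still leaves the choice open after the data are seen.

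A reader might infer that sex was made the stratum because its effect on efficacy was in doubt, since Section 5.1 opens a paragraph with "To address possible sex differences in the use and efficacy of the intervention". That paragraph explains the recruitment mix. Sections 6.2 and 10.7.a give no reason for stratifying. A sex difference in efficacy would also be an interaction, whereas the loss shown here comes from a sex difference in mean change.

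**Conclusion.** The point holds as a gap in specification. The randomisation stratum is in neither primary model as written, and the Aim 4 balance trigger will rarely bring it in. If change differs by sex, the unadjusted standard error is too large, with no bias and no inflated type I error.

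The size rests on three assumptions: a 27:13 sex split, an unstated sex difference in change, and a single-time-point normal outcome standing in for the Aim 3 repeated-measures model. At a 0.8 SD effect the loss runs from nothing to about 8 points of power as the sex difference goes from 0 to 1.0 SD. It is material only from roughly 0.5 SD upward.

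Two stronger readings are not supported. One is that the confidence intervals will be too wide: that follows only if change differs by sex. The other is that planning of the follow-up trial would inherit a wrong SD. The unadjusted SD is a valid marginal SD, and it is merely conservative if that trial adjusts for sex.

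The mismatch between 100 participants in the power statement and 40 in the trial is a separate and larger matter.

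**What to change.** In Section 9.0, state that sex, as the randomisation stratum, is a fixed factor in the Aim 3 repeated-measures model for every symptom and function outcome and in the Aim 4 radiographic model, regardless of observed balance. Say that any treatment effect shown by sex is descriptive, with a 95% confidence interval, given an interaction SE of about 0.68 SD.

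The cost is one sentence and one degree of freedom in each model. Sex is already collected at baseline.
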